Primary Hypothesis:

Our hypothesis is that internal, controlled transverse fracture compression with modern intramedullary rod treatment of transverse tibial shaft fractures will be associated with an increased rate and time to union compared to the traditional methods of dynamic locking and backslapping.

Methods:

Inclusion Criteria

1. Skeletal Maturity
2. Closed or open diaphyseal (shaft) tibia fracture that is axially stable and will tolerate compression without shortening.
3. Treatment with Intramedullary Rod.
4. Fracture compression using one of three methods:
 - a. Dynamic locking.
 - b. Backslapping with dynamic locking.
 - c. Internal rod compression with static locking.
5. Complete inpatient and outpatient medical records and operative notes.
6. Complete radiographic and clinical follow-up for minimum one year.

Exclusion Criteria

1. Skeletally immature.
2. Metabolic Bone Disease
3. Immunosuppression
4. Pathological Fracture (Tumor, Pre-existing Infection)
5. Pre-existing Infection
6. Soft-tissue coverage not obtained within two weeks from time of injury.
7. Use of Negative Pressure Dressing to definitively manage wound.
8. Use of external or implantable bone growth stimulator.

9. Unable to Full Weight Bear immediately post-operative.

Data Points:

1. Age
2. Sex
3. Medical Comorbidity
4. Smoking Status (Yes or No)
5. Closed or Open fracture:
 - a. Wound Size (surface area)
 - b. Wound type (Gustilo Anderson and OTA)
6. Number of Surgical Debridements
7. Time to definitive closure.
8. Soft Tissue Reconstructive Procedure
9. Compartment Syndrome (Yes or No)
10. Fasciotomy (Yes or No)
11. Treatment Method:
 - a. Dynamic locking.
 - b. Backslapping with dynamic locking.
 - c. Internal rod compression with static locking.
12. Union (Yes or No)
13. Time to union (months).
14. Implant complications (Rod or Screw Breaking)
15. Loss of reduction and healing alignment on orthogonal radiographs.
16. Need for subsequent secondary treatment:
 - a. Superficial Infection (Antibiotic Treatment)
 - b. Deep Infection (Surgical Treatment)
 - c. Delayed Union (Exchange rodding, Bone grafting)
 - d. Nonunion (Exchange rodding, Bone grafting)

Methodology:

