Descriptive statistics will be presented as means and standard deviations for continuous variables and as frequencies and percentages for categorical variables. Statistical analysis of categorical variables utilized Fischer's exact test with descriptive statistics reported as frequencies and percentages. For continuous variables, a Mann-Whitney U test was utilized with descriptive statistics reported as means and ranges. Significance set at p value less than or equal to 0.05. All statistical analyses were performed using IBM SPSS version 22 (Chicago, IL, 2013).

Bibliography:

1. Randomized Trial of Reamed and Unreamed Intramedullary Nailing of Tibial Shaft Fractures. *J Bone Joint Surg Am.* 2008;90:2567-2578.
3. Court-Brown CM. Reamed Intramedullary Tibial Nailing: An Overview and Analysis of 1106 Cases. *J Orthop Trauma.* 2004;18:96-101.
4. Blachut PA O'Brien PJ, Meek RN, Broekhuyse HM. Interlocking Intramedullary Nailing With and Without Reaming for the Treatment of Closed Fractures of the Tibial Shaft. *J Bone Joint Surg Am.* 1997;79:640-646.
6. Hammer RR Hammerby S, Lindholm B. Accuracy of Radiographic Assessment of Tibial Shaft Fracture Union in Humans. *Clin Orthop Relat Res.* 1985;199:233-238.

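### Groups formed by call night are compared with unadjusted tests only; pre-specify adjustment for open/closed fracture and smoking, for power and against chance imbalance

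*Combined protocol and SAP*

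**What the plan says.** **Allocation (Methodology).** The method depends on which of three trauma teams is on call on the night the patient presents. The teams follow a strict one-in-three rotation, and each team is tied to one method: A dynamic locking, B backslapping with dynamic locking, C internal rod compression. There is no randomisation or stratification.

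**Patient mix (Inclusion Criteria and Data Points).** Both fracture types are eligible: "Closed or open diaphyseal (shaft) tibia fracture that is axially stable". Data Points lists open/closed status (item 5) and smoking as yes/no (item 4).

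**Comparison (Primary Hypothesis).** Internal compression is to be judged on union and time to union "compared to the traditional methods of dynamic locking and backslapping", which gives the contrasts C vs A and C vs B.

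**Analysis (Statistical Analysis Plan).** Categorical variables get Fisher's "exact test with descriptive statistics reported as frequencies and percentages". The other test is stated as: "For continuous variables, a Mann-Whitney U test was utilized with descriptive statistics reported as means and ranges". The significance level is 0.05. No covariate, regression model or stratified test is named. The software sentence reads: "All statistical analyses were performed using IBM SPSS version 22".

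**The concern.** The trial collects two baseline factors that may affect healing and makes no planned use of them in the treatment comparison. If open fracture and smoking slow union, two things follow.

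- The unadjusted time-to-union comparison has less power than the collected data allow, because the unadjusted hazard ratio is pulled towards 1.
- If one arm happens to receive more open fractures, its result looks worse for that reason alone. The plan has no pre-specified answer, and an adjustment chosen after seeing the imbalance would be open to challenge.

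For union yes/no, the benefit claimed is control of a measured imbalance, not power.

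**Working it through.** The plan states no sample size, union rate, power or covariate effect, so there is no figure of its own to reproduce. Everything below is an illustration on assumed inputs.

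**Inputs from the documents.** Three groups; contrasts C vs A and C vs B; visits at 6, 12, 24 and 52 weeks; alpha 0.05 (taken as two-sided); open/closed and smoking recorded.

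**Assumed.** 35% open with union HR 0.5; 35% smokers with HR 0.6; probability of union at the four visits, for a closed fracture in a non-smoker not yet united, 0.08, 0.35, 0.60 and 0.60; 20, 40 or 60 per arm; one patient per call night. Weaker covariate effects are shown as well.

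**Step 1: how often imbalance arises.** The numbers of open fractures in two arms are independent Binomial(n, 0.35). The exact probability of a gap of at least 15 points is:
- n = 20 (3 or more patients): 0.407
- n = 40 (6 or more): 0.197; with 20% or 50% open, 0.123 or 0.219
- n = 60 (9 or more): 0.103

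**Step 2: what it does when there is no treatment effect, 40 per arm.** The mean gap in the imbalanced trials is 18.8 points.
- Hazard ratio: the expected shift is about 0.5^0.188 = 0.88. Simulation gives 0.882 unadjusted and 1.003 adjusted.
- Union by week 52: a closed fracture in a non-smoker stays ununited with probability 0.92 × 0.65 × 0.40 × 0.40 = 0.0957. Averaging over smoking, union is 1 − (0.65 × 0.0957 + 0.35 × 0.0957^0.6) = 0.852 if closed and 1 − (0.65 × 0.0957^0.5 + 0.35 × 0.0957^0.3) = 0.626 if open. The expected shift is 0.188 × (0.852 − 0.626) = 0.042. Simulation gives −4.2 points crude and 0.0 stratified by open/closed.

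Both shifts are oriented: they compare the arm with more open fractures with the other arm. Taken as C vs A, they average out to HR 1.00.

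**Step 3: type I error, 40 per arm.** Over all trials it is 5.0% for Mann-Whitney and 5.0% for the adjusted permutation test. In the imbalanced trials it is 6.6% and 5.0%. With covariate HRs 0.7 and 0.8, the imbalanced trials show HR 0.93 unadjusted and a Mann-Whitney error of 5.1%.

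**Step 4: power for C vs A.** Each cell shows Mann-Whitney / model without covariates / model with covariates, in percent, with both models tested by permutation.

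| Covariate HRs (open, smoking) | 20 per arm, HR 2.5 | 40 per arm, HR 1.8 | 60 per arm, HR 1.6 |
|---|---|---|---|
| 0.5, 0.6 | 58.6 / 62.4 / 68.7 | 52.2 / 55.9 / 63.5 | 51.1 / 54.0 / 62.3 |
| 0.7, 0.8 | 63.3 / 70.1 / 70.4 | 57.3 / 64.3 / 65.6 | 55.8 / 63.5 / 65.1 |
| 0.85, 0.9 | 64.4 / 72.3 / 70.8 | 58.9 / 67.3 / 66.6 | 57.1 / 65.3 / 65.6 |

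The covariates' own contribution is the third figure minus the second: 6.3, 7.6 and 8.3 points in the first row; 0.3, 1.3 and 1.6 in the second; −1.5, −0.7 and +0.3 in the third. The rest of the gain over Mann-Whitney comes from changing the model.

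**Step 5: standard error.** With covariate HRs 0.5 and 0.6, the SD of the log HR rises with adjustment, from 0.260 to 0.271 at 40 per arm and from 0.379 to 0.422 at 20. The power gain comes from a less attenuated hazard ratio.

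**Step 6: small arms.** With no treatment effect, the adjusted Wald test rejects in about 6.3% to 6.6% of trials at 20 per arm and 7.2% at 15. The permutation test gives 5.0% at 20 per arm.

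**The case against.** **The benefit rests on assumed effects.** This stands. The documents do not say how strongly open fracture or smoking acts. Exclusion Criteria 6 ("Soft-tissue coverage not obtained within two weeks from time of injury") and 7 ("Use of Negative Pressure Dressing to definitively manage wound"), with similar open-wound management in all groups, may weaken the open/closed contrast. With weak effects the covariates add nothing. The possible loss is then small: at most 1.5 points against the same model without them.

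**The dominant threat is elsewhere.** This also stands. Each method belongs to one team, so method and team cannot be separated. With a team effect of HR 1.5 and no device effect, at 40 per arm, false rejection is 28% with Mann-Whitney and 35% with the adjusted test. That is a separate weakness, and no reason to leave a measured imbalance uncorrected.

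**The rotation may not balance the groups.** Partly right. Call night should be unrelated to fracture type or smoking at presentation. But several eligibility items can be judged after the team is known: axial stability, immediate full weight bearing, items 6 and 7 above, and "Complete radiographic and clinical follow-up for minimum one year". Selection through these would be systematic, and adjustment for two factors would not remove it.

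**Stronger readings a reader might infer.**
- That the lack of adjustment makes the planned tests invalid: on this point it does not, since their overall error stays near 5%.
- That the 0.88 is a bias against group C: it is not, because either arm may by chance have more open fractures.
- That adjustment narrows the interval for the hazard ratio: Step 5 shows a slightly larger standard error.
- That the past tense in the Statistical Analysis Plan proves the analysis is finished: the wording is mixed and does not settle it.

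**Conclusion.** The point holds as a recommended improvement. The plan compares groups formed by call night with unadjusted tests only, although two candidate prognostic factors are already collected. Under moderate assumed effects (HRs 0.5 and 0.6) the cost is 6 to 8 points of power for time to union. At 40 per arm, about one trial in five would also carry an uncorrected shift of roughly 0.88 in HR, or 4 points in union, against whichever arm has more open fractures. With HRs 0.7 and 0.8 the power cost is 0 to 2 points, and with weaker effects it is nil. Confidence is medium: the facts about the plan are clear, but sample size, prevalences, union rates and covariate effects are all assumed.

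**What to change.** Before outcome data are analysed, specify the following.

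1. **Time to union:** one discrete-time complementary log-log model on the 6-, 12-, 24- and 52-week visits, with visit intercepts, treatment group (C vs A, C vs B), open vs closed fracture, and smoking yes/no.
2. **Inference:** take each p-value from a permutation test. Compute the contrast's score statistic from the model fitted without that contrast, and reshuffle the labels of the two groups compared. Obtain the HR interval by inverting that test, or by another small-sample method consistent with it.
3. **Call night:** record it if patients sharing a night are to be permuted together. It is not among the listed Data Points.
4. **Union by week 52:** an exact test stratified by open/closed, for the same contrasts. Few nonunions would allow only one stratifying factor.
5. **Support:** keep Fisher's and Mann-Whitney tests as unadjusted analyses.
6. **Limitations to state:** adjustment cannot separate method from call team, and cannot remove selection from eligibility items that can be judged after the team is known.

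If the analysis has already been done, label the adjusted model post hoc.

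**Cost.** New SAP wording, one added data point, and some scripting beyond standard SPSS procedures; both covariates are already collected. There is little or no gain if the factors predict healing weakly. How the 0.05 is shared across contrasts and outcomes is a separate matter that this change leaves as it is.
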